## Participants

30 participants who lost their hearing and received cochlear implants as adults will participate in this study. We will include unilaterally and bilaterally implanted individuals listening with their everyday hearing configuration. Individuals with residual acoustic hearing better than 60 dBA at any audiometric frequency will be excluded to avoid the confounding the study with the effects of bimodal hearing. Participants with residual hearing in the non-implanted ear will inset an earplug into that ear to further ensure the stimuli are inaudible to that ear. The upper age limit on participants will be 80 years of age, to avoid the rising prevalence of dementia at older ages (Piccirillo et al. 2008) while still including a wide age range. We will attempt to recruit equal numbers of men and women, although we will prioritize including all interested participants over achieving parity. All statistical analyses will be conducted with sex as an additional predictor, although we do not expect sex to affect experimental outcomes.

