## Methods

### General methodology for at-home testing

To avoid the risk of transmitting COVID through the lab, experiments will be conducted by participants in their own homes while on a video call with lab staff. At-home testing will enable us to recruit more participants than just those that can commute to the lab. At least 10 participants in this study will be individuals who have previously completed some of these tasks in the lab, to enable comparison of in-lab and at-home performance.

Experiment setup and performance will be conducted through a HIPAA-compliant WebEx video call between the research participant and lab staff. Consent will be administered through the video call using forms available through the Boy Town National Research Hospital REDCap server. If participants have difficulty understanding speech through the video call the text chat feature will be used to communicate to the participant.

Prior to each experimental session, a loudspeaker, external sound card, and sound level meter will be shipped to the participant with set-up instructions. We anticipate that participants will need some assistance setting up equipment, which we provide time for after administering consenting. Once the experimenter verifies that the equipment is properly set up, we will direct them to a YouTube video which plays a speech-shaped noise that has the long-term average spectrum of the speech material and ask them to adjust the volume of their computer until the sound level meter reads 65 dB SPL (slow, A-weighted) at approximate ear-level, following instructions sent with the equipment.

Experiments will be hosted on the website cognition.run. This website hosts behavioral experiments written in JavaScript using the jsPsych library (de Leeuw 2015), which eliminates the need to download or install experimental software. Pre-recorded auditory stimuli are loaded at the start of each task to avoid interruptions due to buffering during playback. Auditory stimuli less than a few seconds in length can be dynamically generated at the start of each trial, which enables adaptive psychophysical testing. Visual stimuli are precisely timed, with stimulus transitions occurring within a few milliseconds of the intended transition time. Button and keyboard responses are recorded without any personally identifying information in a database on the website, and verbal responses will be recorded through the WebEx video call and stored on a secure database at Boys Town.

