### Step 2: Predict speech recognition accuracy in quiet

We expect both modulation detection thresholds to be significant predictors of sentence recognition accuracy, which will account for approximately half of the variance. We will compare the likelihood of generalized linear regression models which include only modulation detection thresholds against models which also include the memory components identified in step 1 to determine if these memory components are significant predictors of speech recognition in quiet. We will verify that modulation detection thresholds and working memory task performance are not correlated, as we found in participants with cochlear implants ( $r = -0.36$ ,  $r = -0.15$  for spectral and temporal threshold correlations with digit span,  $p > 0.10$ ).

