### Step 3: Test for a mediating relationship of stream segregation for speech recognition in competing speech

We will extrapolate the predictor model for speech recognition in quiet developed in step 2 to the case of speech recognition in competing speech. If the model performs as well for speech in speech as it does for speech in quiet, we would infer that two-talker speech maskers do not introduce meaningful variability into speech recognition outcomes and stop here. If the speech in quiet model is a worse fit, we will add stream segregation to the predictor model and test whether it predicts unique variance in speech recognition accuracy in competing speech. This would demonstrate that stream segregation is a distinct aspect of speech recognition in the presence of competitors. Finally, to complete the mediator analysis we would test whether modulation detection thresholds and memory factors are significant predictors of stream segregation ability.

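### Unilateral and bilateral implant users are pooled but no model includes implant configuration, so a two-implant advantage shared by segregation and speech-in-speech accuracy could be credited in part to segregation

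*Protocol*

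**What the plan says.** The Protocol (Participants) sets the sample: "30 participants who lost their hearing and received cochlear implants as adults will participate in this study". On configuration it says: "We will include unilaterally and bilaterally implanted individuals listening with their everyday hearing configuration". It gives no quota, stratification or common one-ear test condition.

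The same section treats a neighbouring feature of hearing configuration as a confounder and controls it by design. "Individuals with residual acoustic hearing better than 60 dBA at any audiometric frequency will be excluded to avoid the confounding the study" with bimodal hearing, and "Participants with residual hearing in the non-implanted ear will inset an earplug into that ear". Nothing comparable is done for one implant against two.

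The only covariate added to the analyses is sex: "All statistical analyses will be conducted with sex as an additional predictor, although we do not expect sex to affect experimental outcomes".

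The SAP models contain no configuration term. Step 2 compares "models which include only modulation detection thresholds against models which also include the memory components identified in step 1". In Step 3, if the quiet model fits worse in competing speech, "we will add stream segregation to the predictor model and test whether it predicts unique variance in speech recognition accuracy in competing speech". The last part of Step 3 regresses segregation on the thresholds and memory factors. No subgroup or sensitivity analysis by configuration appears in either document.

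**The concern.** Sound reaches participants through the shipped loudspeaker, so the number of implants in use can bear on every auditory measure: sentence recognition in quiet and in masking, both modulation thresholds, the spoken digit tasks and the segregation task. Configuration is therefore a possible common cause of the mediator and the outcome, and it lies outside the model.

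Step 3 draws its main inference from segregation predicting unique variance in speech-in-speech accuracy. An unmodelled common cause can produce that result with no direct link between the two. The planned analyses would not reveal it.

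The size of the coefficient also matters, not only its p-value. The Protocol (Sample Size and Power Analysis) says the pilot's goal is to estimate the indirect-path effects for later work. It gives 34 participants for path effects of 0.59 and 71 for 0.39. A change of 0.59 − 0.39 = 0.20 in the assumed effects thus roughly doubles the next study, so a spurious contribution of 0.1 to 0.2 would matter on that scale.

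**Working it through.** **The plan's own figure.** The Protocol states 29 participants for r = 0.5, α = 0.05 and 80% power (written there as β). With Fisher's z, two-sided:

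N = ((1.960 + 0.842) / atanh(0.5))² + 3 = (2.802 / 0.549)² + 3 = 29.01.

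This agrees with 29. The one-sided version gives 23.5 and does not. The two-sided convention is used below.

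**Inputs from the documents.** n = 30 (Protocol, Participants). The Step 3 model holds segregation, two modulation thresholds, the retained memory components (taken as two) and sex.

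**Assumed inputs, because the documents give none.** The bilateral share p is 0.3 or 0.5 (9 or 15 of 30). Having two implants shifts segregation by dS and the outcome by dY, each from 0 to 1 within-group SD. These shifts are what remains after the modelled predictors are taken into account.

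**Spurious correlation** between segregation and outcome when neither affects the other:

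r = p(1−p)·dS·dY / √[(1 + p(1−p)dS²)(1 + p(1−p)dY²)].

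For p = 0.5 and dS = dY = 1: 0.25 / 1.25 = 0.20. For p = 0.5 and dS = dY = 0.5: 0.0625 / 1.0625 = 0.059. For p = 0.3 and dS = dY = 1: 0.21 / 1.21 = 0.174.

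**Rejection rate** of the segregation coefficient at nominal 5%, from least-squares simulation (20,000 replicates, n = 30, no true segregation effect, the model above, with and without a configuration term):

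| p | dS | dY | spurious r | without term | with term |
|---|---|---|---|---|---|
| 0.3 | 0 | 0.8 | 0 | 5.1% | 5.2% |
| 0.3 | 0.8 | 0 | 0 | 5.0% | 4.9% |
| 0.3 | 0.5 | 0.5 | 0.050 | 5.6% | 5.2% |
| 0.3 | 0.8 | 0.8 | 0.118 | 8.3% | 5.1% |
| 0.3 | 1 | 1 | 0.174 | 13.2% | 4.9% |
| 0.5 | 0 | 0.8 | 0 | 5.0% | 4.9% |
| 0.5 | 0.8 | 0 | 0 | 5.1% | 5.0% |
| 0.5 | 0.5 | 0.5 | 0.059 | 5.7% | 4.8% |
| 0.5 | 0.8 | 0.8 | 0.138 | 9.6% | 5.0% |
| 0.5 | 1 | 1 | 0.200 | 16.1% | 5.0% |

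The error rate rises only when configuration shifts both measures. The configuration term removes the excess in every scenario.

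**Cost of the term.** Power for a partial r of 0.5 with k covariates is Φ(0.549·√(27 − k) − 1.960). From k = 0 to 1 it falls from 81.4% to 80.0%. From k = 5 (two thresholds, two memory components, sex) to k = 6 it falls from 73.1% to 71.1%.

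**The case against.** The case that this is small is good, and most of it stands.

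- **The segregation score is a within-person difference** between the alternating-pitch conditions and the same-pitch baseline (Protocol, Predictor 3). A general gain in digit recall from a second implant cancels. Only a differential gain in using the pitch cue survives, so equal shifts on both measures are hard to justify. With assumed shifts of 0.3 SD on segregation and 0.5 SD on the outcome and a 15/15 split, the formula gives 0.0375 / √(1.0225 × 1.0625) = 0.036.
- **Playback limits the gain on the outcome.** The kit includes "a loudspeaker, external sound card, and sound level meter will be shipped to the participant with set-up instructions". With one loudspeaker, target and masker apparently share a location, so benefit from spatial separation should be small. Other two-ear benefit remains possible.
- **The thresholds carry part of the effect.** They are measured in the same configuration and accounted for R² = 0.64 of sentence accuracy in the preliminary data. That figure is for quiet, so it does not rule out a residual effect in competing speech.
- **Degrees of freedom are scarce** in a 30-person pilot.

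These points limit the likely size. They do not show that the residual effect is zero.

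A reader might go further in three ways that the documents do not support. One is to take 13–16% as the expected error rate; it needs a residual 1 SD shift on both measures, which nothing in the documents suggests. Another is to say that the threshold or memory coefficients are biased too; the calculation covers only the segregation coefficient. The third is to put configuration in place of sex; the Protocol commits to sex in every analysis, and configuration has no documented effect that would justify the swap.

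**Conclusion.** The omission is real and cheap to close. Configuration is pooled at enrolment, left free at testing and absent from the models, although the Protocol treats bimodal hearing as a confounder. Bias in Step 3 requires that two implants improve both use of the pitch cue and speech-in-speech accuracy beyond what the thresholds capture. An effect on the outcome alone costs precision only.

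Under the assumed shifts and bilateral shares of 30–50%, the false-positive rate for segregation runs from about 6% at 0.5 SD to 13–16% at 1 SD. The lower part of that range is the more plausible, given the within-person score and the single loudspeaker. The documents supply neither the bilateral share nor the effect, so this is a plausible alternative explanation that the plan leaves open, not a demonstrated bias.

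**What to change.** In the Protocol (Participants) and in SAP Steps 2 and 3:

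1. Record implant configuration as used in testing (unilateral or bilateral).
2. Add it as a binary predictor alongside sex, and keep sex as the Protocol commits.
3. Report both Step 3 models, the one from segregation to outcome and the one predicting segregation, with and without the configuration term.

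Configuration is known at enrolment, so no new visit, test or participant is needed. The price is the one degree of freedom costed above. Reporting both versions lets the reader see whether the segregation result depends on the term.

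Suggested wording: *Implant configuration as used in testing (unilateral or bilateral) will be included with sex as a predictor in the Step 2 and Step 3 models. Step 3 results will be reported with and without this term.*

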## Methods

### General methodology for at-home testing

To avoid the risk of transmitting COVID through the lab, experiments will be conducted by participants in their own homes while on a video call with lab staff. At-home testing will enable us to recruit more participants than just those that can commute to the lab. At least 10 participants in this study will be individuals who have previously completed some of these tasks in the lab, to enable comparison of in-lab and at-home performance.

Experiment setup and performance will be conducted through a HIPAA-compliant WebEx video call between the research participant and lab staff. Consent will be administered through the video call using forms available through the Boy Town National Research Hospital REDCap server. If participants have difficulty understanding speech through the video call the text chat feature will be used to communicate to the participant.

Prior to each experimental session, a loudspeaker, external sound card, and sound level meter will be shipped to the participant with set-up instructions. We anticipate that participants will need some assistance setting up equipment, which we provide time for after administering consenting. Once the experimenter verifies that the equipment is properly set up, we will direct them to a YouTube video which plays a speech-shaped noise that has the long-term average spectrum of the speech material and ask them to adjust the volume of their computer until the sound level meter reads 65 dB SPL (slow, A-weighted) at approximate ear-level, following instructions sent with the equipment.

Experiments will be hosted on the website cognition.run. This website hosts behavioral experiments written in JavaScript using the jsPsych library (de Leeuw 2015), which eliminates the need to download or install experimental software. Pre-recorded auditory stimuli are loaded at the start of each task to avoid interruptions due to buffering during playback. Auditory stimuli less than a few seconds in length can be dynamically generated at the start of each trial, which enables adaptive psychophysical testing. Visual stimuli are precisely timed, with stimulus transitions occurring within a few milliseconds of the intended transition time. Button and keyboard responses are recorded without any personally identifying information in a database on the website, and verbal responses will be recorded through the WebEx video call and stored on a secure database at Boys Town.

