#### Predictor 1: Auditory resolution

Preliminary data from 20 participants with cochlear implants tested in the lab indicates that spectral and temporal modulation detection thresholds predict PRESTO sentence recognition accuracy in quiet. In a generalized linear regression model, spectral and temporal modulation detection thresholds accounted for  $R^2 = 0.64$  of the variance in recognition accuracy (spectral  $\beta = -0.76$ , temporal  $\beta = -0.47$ ). We will repeat these tasks in this study.

Modulation detection thresholds will be measured with a three-interval, three-alternative forced-choice task. The carrier signal is a 60 dB SPL, 400 ms long noise burst with energy between 350 and 6500 Hz (selected to match the stimuli in Litvak et al. 2007), gated on and off with 20 ms  $\sin^2$  ramps. Carriers are modulated in the target interval and was unmodulated in the other two intervals. Feedback is given after each trial. In the temporal modulation detection task, the target interval is sinusoidally amplitude-modulated at a 100 Hz rate, which has been previously shown to correlate with speech recognition in listeners with cochlear implants when presented via direct stimulation (Fu 2002; Luo et al. 2008) and via a loudspeaker (Won et al. 2011). In the spectral modulation detection task, the target interval is spectrally modulated at 0.5 ripples per octave, which has been previously shown to correlate with speech recognition when presented via a loudspeaker (Anderson et al. 2012; Litvak et al. 2007; Saoji et al. 2009). Carrier level for every interval is randomly varied between -3 and +3 dB Sound Pressure Level (SPL) to diminish the availability of loudness differences between modulated and unmodulated intervals (McKay and Henshall 2010).

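### The listening level is set once on a YouTube video but the tests play from cognition.run, with no stated level match and no meter reading on the test site

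*Protocol*

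**What the plan says.** All of the level setting is in the Protocol, under General methodology for at-home testing.

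- Hardware: "a loudspeaker, external sound card, and sound level meter will be shipped to the participant with set-up instructions". No computer is listed, so the computer appears to be the participant's own.
- Sequence: the level step follows a staff check of the set-up ("Once the experimenter verifies that the equipment is properly set up"). In that step "we will direct them to a YouTube video which plays a speech-shaped noise that has the long-term average spectrum of the speech material", and participants are asked to "adjust the volume of their computer until the sound level meter reads 65 dB SPL (slow, A-weighted) at approximate ear-level", using a written instruction sheet that is not among the documents.
- Test playback: "Experiments will be hosted on the website cognition.run". Recorded sounds are preloaded there, and "Auditory stimuli less than a few seconds in length can be dynamically generated at the start of each trial".

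Under Predictor 1: Auditory resolution, the modulation tasks are specified at an absolute level: "The carrier signal is a 60 dB SPL, 400 ms long noise burst with energy between 350 and 6500 Hz". No separate calibration is described for them.

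Neither document states that the YouTube noise and the cognition.run stimuli share a digital reference level. Neither describes a reference sound on the test site, a meter reading during or after testing, or a recorded reading. The SAP does not use level in any step.

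**The concern.** The meter reading certifies the level of the YouTube noise. It certifies the level of the test sounds only if everything upstream of the computer volume is equal on the two sites. If the video page attenuates its sound, the participant makes up the loss with the computer volume, and every sound on the test page is then too loud by that amount. If the test page is the quieter of the two, the error runs the other way. The offset would be constant within a home, could differ between homes, and would leave no trace in the data.

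Two features of this study make that worth closing. First, one offset reaches both sides of the regressions: modulation thresholds and spoken-digit tasks as predictors, and speech in quiet as an outcome. If scores depend on level, observed associations could be weakened or strengthened. The Protocol's Sample Size and Power Analysis section says the pilot is meant to estimate effect sizes for later work, so distortion in either direction matters. Second, the SAP opens by saying that the analysis is staged to confirm that previous findings replicate at home. A level difference is one explanation for a failed replication that the planned data could not examine.

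**Working it through.** **1. The two playback paths, in outline**

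- Calibration: YouTube noise, video-page gain, computer volume, sound card, loudspeaker, meter reading of 65 dB.
- Testing: cognition.run sound, test-page gain, computer volume, same sound card, same loudspeaker, no meter reading.

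From the computer volume onward the paths are shared. The source's digital level and the page gain are not. The 65 dB setting and the 60 dB SPL carrier hold during testing only if those two unshared elements are matched.

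**2. Size of a possible offset (assumed; no gain is given in the documents)**

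Let g be the amplitude gain of the video page relative to the test page, with source levels otherwise matched. The offset in the tests is −20 log10(g).

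- g = 1: 0 dB.
- g = 0.5: 6.0 dB. Nominal speech becomes 65 + 6 = 71 dB and the carrier 60 + 6 = 66 dB SPL.
- g = 0.25: 12.0 dB. These become 77 dB and 72 dB SPL.

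These values only show how the formula behaves. They are not estimates.

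**3. Which measures are exposed**

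An offset d raises target and masker alike: (target + d) − (masker + d) = target − masker = +5 dB. The ratio that defines the primary condition is unchanged. What does not cancel is absolute level: PRESTO in quiet, the modulation carrier, the tasks with spoken digits (serial digit span, running digit span, stream segregation) and overall audibility. Reading span, free recall and digit updating are presented visually and are not exposed.

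**4. The plan's own sample size**

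Inputs from Sample Size and Power Analysis: r = 0.5, alpha 0.05, power 0.80 (written there as beta). By Fisher's z, two-sided:

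n = ((1.960 + 0.842) / atanh(0.5))² + 3 = (2.802 / 0.549)² + 3 = 29.01.

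The stated 29 is reproduced (one-sided would give 23.5). At the planned n = 30, power is Φ(0.549 × √27 − 1.960) = 0.814.

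**5. What level differences could do to a correlation (assumed ranges)**

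The documents give no between-home spread of level and no slope of score on level. If level adds a fraction v of extra variance to the speech score alone, r becomes 0.5 / √(1 + v):

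| v | r | Power at n = 30 | N for 80% power |
|---|---|---|---|
| 0 | 0.500 | 0.81 | 29 |
| 5% | 0.488 | 0.79 | 31 |
| 10% | 0.477 | 0.77 | 33 |
| 20% | 0.456 | 0.73 | 36 |
| 30% | 0.439 | 0.69 | 39 |

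To tie v to decibels, assume a score SD of 20 points, so v = (slope × level SD / 20)².

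- 1 point per dB and a level SD of 3 dB: v = (3/20)² = 2%, power 0.80.
- 2 points per dB and a level SD of 5 dB: v = (10/20)² = 25%, power 0.71.

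If instead level adds the same fraction v to predictor and score and acts to reinforce their association, r becomes (r + v) / (1 + v). For v = 10% and 20%, a true 0.5 becomes 0.55 and 0.58, and a true 0 becomes 0.09 and 0.17.

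**The case against.** The best defence is that the step may already work. Participants adjust the computer volume, which both sites share. The loudspeaker and sound card are supplied, staff verify the set-up and are on the video call, and the unseen instruction sheet may fix the player's volume. The documents describe no player control at all, so a video-page gain below full is an assumption. With matched sources the offset is 0 dB. Even with some offset, the milder case above moves power only from 0.81 to 0.80. At least 10 of the 30 participants will also have in-lab results on some tasks.

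Most of this stands as a limit on size. It does not close the gap: the set-up check comes before the noise is played, shared hardware does not equalise the two web sources, and the in-lab comparison could reveal an average shift but could not attribute it to level or correct a given home.

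A reader might infer more, and the documents do not support it:

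- **That levels will be wrong by 6 or 12 dB.** Those figures follow only from chosen values of g.
- **That the primary outcome is compromised.** Its +5 dB ratio does not depend on overall gain, and no slope of score on level is given.
- **That the residual-hearing safeguard fails because of the two sites.** The Protocol says "Individuals with residual acoustic hearing better than 60 dBA at any audiometric frequency will be excluded", and the nominal 65 dB A-weighted level already exceeds that limit by 5 dB with perfect calibration. An earplug is also planned for a non-implanted ear with residual hearing.
- **That the −3 to +3 dB variation in the modulation tasks absorbs the offset or is a yardstick for it.** It changes level between intervals to reduce loudness cues; a constant offset is a different quantity.
- **That a stated sample size is wrong.** The 29 is reproduced.

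**Conclusion.** The point holds as a gap in the described procedure with a cheap remedy. It is not evidence of an error that will occur. As written, the level during testing rests on an unstated and unchecked equality between two playback sources. The consequence is a possible constant, unrecorded, home-specific offset, of unknown size and possibly 0 dB, acting through absolute level only. Under the assumed ranges above, the effect on a correlation of 0.5 runs from negligible (2% added variance, power 0.80) to moderate (25%, power 0.71), with upward bias also possible if predictor and score share the offset. Because no level is recorded, no later analysis could detect or correct it home by home, which is the reason to act before data collection.

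**What to change.** In General methodology for at-home testing, replace the YouTube video with the same speech-shaped noise played from a cognition.run page, through the same audio code and at the same digital reference level as the test stimuli. Have the participant set 65 dB there. Record the meter reading at that point and again, with the same noise, after the auditory tasks. State in the Protocol that the noise, the speech material and the 60 dB SPL carrier are referred to that common digital level.

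This removes the dependence on matched page gains, shows any change in level over the session, and leaves a recorded level for each home that a sensitivity analysis could use.

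The cost is one uploaded sound file, a changed instruction and about one minute per session. The meter is already in the home and staff are already on the call, so no further equipment or staffing is needed.
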